15.0 Risks to Subjects*

15.1 Risks to human subjects in the present study are believed to be minimal. Nevertheless, precautions will be taken to minimize participants' risk in the proposed study. All individuals will be informed of the general nature of the investigation and the types of assessments and procedures. Participants will be given an opportunity to have any questions answered to their satisfaction and then will be asked to sign an informed consent statement prior to participating in the project. The specific potential risks involved in the proposed investigation are enumerated below.

There are two main areas of risk:

1) Self-report Measures: Some participants may be hesitant to record their social anxiety and/or depressive symptoms on assessment forms. It is possible that questionnaires relating to social anxiety, depression, and perceived loneliness could lead to emotional discomfort for some participants.

2) Confidentiality: We will be collecting information about the participant that could cause social and psychological risk if released inappropriately.

The above areas of risk will be minimized by the following procedures:

1) Participants will be made aware that they are free to omit questions they feel uncomfortable answering and are free to terminate their participation at any time during the study without penalty. While some participants may be hesitant to answer the assessment forms, others may derive benefit from the self-assessment as it could increase their awareness of the relationship between their symptoms and environmental, cognitive, and interpersonal factors. Participants will be encouraged to contact study staff at any point during the study if they have questions or concerns. Referrals to appropriate clinical services (e.g., FSU Psychology Clinic, the Anxiety and Behavioral Health Clinic) will be provided for any participants seeking treatment. All research staff will be trained to deal with sensitive clinical issues and will be available during the assessment process should participants need assistance.

2) Breach of confidentiality is highly unlikely. Researchers will emphasize that information obtained during the study is confidential and will be used solely by research staff for research purposes. No data form will ever have a participant's name on it. All records will be kept in locked files and secure servers and it will only be available to the necessary research personnel who know about human participant protection guidelines. A cross index of identity information will be kept in a separate location. In addition, all data will contain only a codified Identification Code, all assessment procedures will be closely supervised, and staff will be trained and reminded of the need to keep all information confidential. No names will be used in presenting the data in lectures, seminars, and papers. No individual responses will be reported in any publications. Information will be released only with the written consent of the participant. Having all information collected and handled by research staff trained to deal appropriately with sensitive clinical issues will minimize potential risk of loss of confidentiality. All information will be treated as confidential material and will be available only to research and clinical staff. The Key-file associating Identification Codes with identifying information will be destroyed once data collection is complete. We have used this approach with hundreds of participants in the past and have never had any problems with a breach of confidentiality.

16.0 Potential Benefits to Subjects*

16.1 A direct benefit to participants is that they will be entered in a raffle for 10 \$20 gift cards. We anticipate participants will have 1 in 10 chance or greater of receiving a gift card.

Based on previous research, we anticipate, the safety behavior fading group may benefit from the study, as it is possible that reducing safety behaviors may result in reductions in symptoms and an increase in emotional disclosure.

17.0 Data Management* and Confidentiality

17.1 *2 X 2 mixed model ANOVAs will be conducted to evaluate the effect of the manipulation on study variables of interest.*

17.2 *Subjects' names and email addresses will be recorded upon their consenting to participate and used to send participants reminders about appointments. Further, participants in the SB Fade group will receive daily emails/texts during the two assessment weeks to remind them to complete their Behavior Checklist each day. However, no names or direct identifiers will be linked with the data collected over the course of the study. Each participant will be assigned a unique, codified Identification Code that is unrelated to the participants' identifying information. All questionnaires will be labeled using their codified Identification Code. The Key-file associating Identification Codes with participant names, email addresses, and phone numbers will be kept by the principal investigator separate from all other study data and consent forms in a secured file. Email addresses are needed in order to send links to and reminders for the online appointments. Phone numbers are needed in order to send daily text message reminders to participants in the SB Fade condition. If an individual is unable or unwilling to supply their phone number, daily reminders will be sent to their email address. All study data will be stored in de-identified databases in password protected files on encrypted computers.*

No individual will ever be publicly identified. We will only report results that have been averaged over participants. No records or assessment information will be released to any other person. All identifying information will be deleted after data collection is complete.

Participants will be informed that there are certain situations in which we may break confidentiality. If during the study we learn about child neglect, child or elder abuse, or that someone is a clear, serious, and direct harm to self or others, we may report the information to appropriate authorities, including the police or an emergency medical facility. Such a possibility is therefore explicitly stated in the consent document. All data and paperwork will be protected to the extent provided by law.

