1.0 Study Summary

Study Title	Safety Behavior Fading Intervention for Social Anxiety
Study Design	Randomized Control Trial
Primary Objective	To investigate the efficacy of a text message based safety behavior fading paradigm.
Secondary Objective(s)	Explore the effect of safety behavior fading on: 1) Levels of emotional disclosure. 2) Reductions in levels of perceived loneliness.
Research Intervention(s)/ Investigational Agent(s)	1) A control condition where participants are asked to participate in healthy behaviors 2) A safety behavior fading condition in which participants receive reminders to change their behavior.
Study Population	Adults aged 18-65
Sample Size	500
Study Duration for individual participants	Approximately 4 hours across a 4 week period.
Study Specific Abbreviations/ Definitions	

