2.0 Objectives*

- 2.1 *The current study aims to explore the efficacy of a text message based Safety Behavior Fading Intervention compared to a control intervention.*
- 2.2 *We hypothesize that individuals practicing safety behavior fading will exhibit (1) decreased social anxiety symptoms and report (2) increased levels of emotional disclosure, and (3) greater reductions of perceived loneliness compared to the control group.*

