6.0 Procedures Involved*

6.1 Participants will be recruited through online postings.

Once they sign up, all participants will be asked to provide informed consent before participating in the current study. After consenting, the participant will complete the first battery of self-report measures. If the participant scores a 30 or lower on the SPIN, they will not be eligible to participate

If they score a 30 or above on the SPIN and meet all eligibility criteria, participants will be randomly assigned to one of two experimental conditions: Safety Behavior (SB) Fading Condition or control condition. During this pre-assessment virtual appointment, participants will complete a questionnaire battery assessing related symptoms and concerns, as well as safety behaviors. Participants in the SB fade condition will select five behaviors from their completed Safety Avoidance Frequency Examination (SAFE) that they engage in the most. They will be informed that the researchers are interested

in the extent to which people can engage in these behaviors less than they normally do on a daily basis, for two weeks. Participants in the “healthy behaviors” group will be told they will be sent a checklist of healthy behaviors.

Participants will also receive instructions regarding how to complete their daily safety behavior monitoring checklist. They will receive 14 checklists via text over the course of the next two weeks (assessment period). Daily checklists will take roughly 5-minutes each.

At the end of four weeks all participants will be sent a second set of questionnaires via email to complete.

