
They will then complete the Credibility/Expectancy Questionnaire (CEQ; Devilly & Borkovec, 2000).

twp-week assessment period:

Component 3: Safety Behavior Checklist (completed daily)

Post-treatment:

Component 4: Self-Report Assessments – Participants will complete a battery of self-report measures that assess relevant constructs. This battery will include all items from Component 1.

Component 7: Debriefing – All participants will be informed of the actual, full study purpose.

One month follow-up:

Component 8: Self-Report Assessments – Participants will complete a battery of self-report measures that assess relevant constructs. This battery will include all items from Component 1

6.3 *The potential risks associated with participation in this study appear to be minimal (see below). Nevertheless, precautions will be taken to minimize participants' risk in the proposed study. All individuals will be informed of the nature of the investigation and the types of assessments and procedures. Participants will be asked to sign an informed consent statement prior to participating in the project. Several safeguards for maintaining participant confidentiality will also be in place (see below). In addition, referrals to appropriate clinical services (e.g. FSU Psychology Clinic) will be provided for any participants seeking treatment.*

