9.0 Study Timelines*

9.1 The total duration of an individual subject's participation in the study is 6 weeks. This will include an initial questionnaire battery, four week manipulation assessment period, and the post-treatment questionnaire's and one month follow up. We predict that it will take roughly 12-18 months to enroll all study subjects.

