10.0 Subject Population*

10.1 Adults aged 18-65 recruited from across the United States

10.2 Inclusion Criteria: The primary inclusion criteria for this study will be elevated social anxiety symptoms as defined by a score of 30 or higher on the SPIN. The only software/hardware requirements are that participants have access to a smartphone or computer that is connected to the internet.

Exclusion Criteria: 1) Score of 29 or lower on the SPIN, 2) Currently receiving treatment (therapy, counseling, etc.) for anxiety or depression, 3) If applicable, unstable psychiatric medication usage any time over the past 4 weeks.

10.3 We will not include: Adults unable to consent, Individuals who are not yet adults (infants, children, teenagers), Pregnant women, or Prisoners.

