14.0 Withdrawal of Subjects*

14.1 Participants will be withdrawn if there are circumstances that severely compromise the integrity of their data such as experimenter error, or if they do not meet eligibility criteria.

14.2 Participants are allowed to withdraw from participation in the study at any point, and data collection will stop at that point. Participants will be consulted as to whether or not they want their data removed from the final dataset.

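### The only stated analysis, 2 × 2 mixed ANOVAs, is on its natural reading a change-score test: valid, but adjusting for the baseline score would be at least as precise at no cost

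*Protocol*

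**What the plan says.** The analysis is stated once in the protocol, in section 17.1: "2 X 2 mixed model ANOVAs will be conducted to evaluate the effect of the manipulation on study variables of interest". Section 4.1 lists endpoints as not applicable, and no section mentions baseline adjustment.

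The surrounding text supports reading 2 × 2 as arm by time. Section 6.1 randomises to two conditions. Section 2.2 frames the loneliness hypothesis as a difference in change: "greater reductions of perceived loneliness compared to the control group". Section 6.2 lists SPIN, the loneliness scale and the two disclosure scales in Component 1, before the treatment rationale is given. For the later batteries it says "This battery will include all items from Component 1". The same scales are therefore available before and after the intervention.

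Entry requires "elevated social anxiety symptoms as defined by a score of 30 or higher on the SPIN" (section 10.2), so the baseline of the social anxiety outcome is selected from above. The stated total is 500 (section 12.1).

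**The concern.** A two-arm, two-occasion mixed ANOVA subtracts the baseline score with a fixed coefficient of 1. When the later score tracks baseline with a slope below 1, full subtraction adds baseline noise to the comparison. A slope above 1 also loses precision. Entering the baseline score as a covariate lets the data set the coefficient.

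What is at stake is precision: the same 500 participants may deliver the information of a smaller trial analysed with adjustment. A lesser point is that each 2 × 2 model holds only two of the three occasions in section 6.2. Effects at post-treatment and at one month would then need separate models, which the plural ANOVAs allows.

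**Working it through.** **Inputs.** From the protocol: two randomised arms (6.1), the same scales at baseline and later (6.2), SPIN of at least 30 at entry (10.2), N = 500 (12.1). Assumed, because the protocol does not give them: equal allocation; pre-post correlation r from 0.4 to 0.9; ratio q of later SD to baseline SD from 0.8 to 1.2; and where the SPIN cut falls in the unselected population (z = -1, 0 or 1). Both r and q refer to the unselected population. The plan has no precision or power figure to reproduce; 500 serves only as a scale.

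**Step 1: what the ANOVA tests.** With two arms and two occasions, the arm-by-time F equals the squared t-test on change scores. In a simulated dataset the interaction F was 8.0708 and the change-score t was -2.841, whose square is 8.071.

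**Step 2: variance comparison.** Let the baseline SD be 1, the later SD q and the slope b = rq. Let k be the share of baseline variance left after selection.

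- Change score: k(1 - rq)² + q²(1 - r²)
- Baseline-adjusted: q²(1 - r²)
- Ratio: 1 + k(1 - rq)² / [q²(1 - r²)]

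The second term of the ratio is never negative and is zero only at rq = 1. At q = 1 the ratio is 1 + k(1 - r)/(1 + r). Estimating the slope costs the adjusted analysis a factor of about 1 + 1/(N - 4), which is 1 + 1/496, or 0.2%.

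**Step 3: selection on SPIN.** For a normal score cut from below at z, k = 1 + zλ - λ², where λ is the normal density at z divided by the upper tail area. This gives k = 0.630, 0.363 and 0.199 at z = -1, 0 and 1; k = 1 without selection. The SPIN figures take the score that is cut at 30 as the baseline.

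**Step 4: results at equal SDs (q = 1).** Example at r = 0.5: untruncated, 1 + 0.5/1.5 = 1.333, so 500 by change score is worth 500/1.333 = 375 by adjustment. For SPIN cut at the mean, 1 + 0.363 × 0.333 = 1.121.

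| r | Excess variance, untruncated (adjusted N that 500 is worth) | SPIN, z = -1 | z = 0 | z = 1 |
|---|---|---|---|---|
| 0.4 | 43% (350) | 27% | 16% | 9% |
| 0.5 | 33% (375) | 21% | 12% | 7% |
| 0.7 | 18% (425) | 11% | 6% | 4% |
| 0.8 | 11% (450) | 7% | 4% | 2% |
| 0.9 | 5% (475) | 3% | 2% | 1% |

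**Step 5: unequal SDs, r = 0.4 to 0.7.** At q = 0.8 the excess is 59 to 86% untruncated and 12 to 54% for SPIN. At q = 1.2 it is 3 to 22% and 1 to 14%.

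**Step 6: loneliness and disclosure.** The untruncated figures are upper bounds if these outcomes correlate with SPIN. With correlation ρ, k = 1 - ρ²(1 - k for SPIN), assuming the later score depends on SPIN only through its own baseline. For ρ = 0.3 to 0.5, r = 0.4 to 0.7 and q = 1, the excess is 14 to 41%.

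**Step 7: simulation at N = 500.** With no truncation, baseline SD 1 and residual SD 0.8, the variance of the adjusted estimate over that of the change score was 0.63, 0.79, 0.95 and 1.004 at slopes 0.4, 0.6, 0.8 and 1.0. With baseline cut at 30 (assumed population mean 25, SD 15, residual SD 10) it was 0.81, 0.92, 0.97 and 1.001. Neither estimator showed bias.

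**The case against.** The strongest reply is that the planned test is conventional and valid, and that covariates are usually set in a statistical analysis plan, which is not at hand. The first half stands: nothing in 17.1 is invalid. The second half would dispose of a complaint about missing detail, but the protocol does name a method, and that method subtracts baseline where adjustment would do at least as well.

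Three further objections stand as limits. The factors and tested term are inferred. (Testing the arm main effect would not rescue the plan: it averages pre and post, and in the Step 1 dataset it gave t = -0.06.) The size of the gain rests wholly on assumed r and q, and it is small at high correlation. That the gain is larger for loneliness and disclosure than for SPIN holds only at the same r and q; across different values the ranges overlap.

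A reader might infer more than this:

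- **Bias from the SPIN cut.** Selecting high scorers makes regression to the mean likely, but under randomisation it is expected equally in both arms, so the arm comparison is not biased.
- **A missing-data fault.** Section 14.2 says "Participants will be consulted as to whether or not they want their data removed from the final dataset", but nothing here depends on dropout or data removal, and their handling may be in the analysis plan.
- **An underpowered trial.** The protocol states no power target or effect size, so none can be shown to be missed.

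**Conclusion.** The point holds as a free improvement in efficiency. On the arm-by-pre/post reading, the stated ANOVA is a change-score test that is valid but never more precise than baseline adjustment. This sets aside about 0.2% at N = 500 and assumes equal allocation or a common slope; the protocol does not state the allocation ratio.

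At equal SDs and r from 0.4 to 0.9, the loss is about 5 to 43% in variance for an untruncated baseline and about 1 to 27% for SPIN. It vanishes as the slope approaches 1 and grows when the later SD is smaller than the baseline SD. The documents cannot place the trial within these ranges. They do not support calling the analysis wrong, biased or inadequate.

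**What to change.** In section 17.1, replace the 2 × 2 ANOVA with wording such as:

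> For each outcome and each later assessment, an analysis of covariance of the later score on arm, adjusted for the baseline score of the same outcome. The treatment effect is the adjusted difference between arms at that assessment.

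If both later batteries in 6.2 are kept, one repeated-measures model of the post-baseline scores may be used instead, with arm, time, arm-by-time, baseline and baseline-by-time. The text must then state the treatment effect as the adjusted arm difference at each named time point. In that model the arm-by-time term only asks whether the effect differs between the later assessments; it is no longer the treatment test.

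The cost is rewording 17.1. No extra data, visits or participants are needed. A participant without a baseline score drops out of the analysis of covariance unless the score is imputed, but such a participant has no change score either.

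Separately, and whichever analysis is used, the protocol must reconcile the number and timing of the later batteries. Section 1.0 gives "Approximately 4 hours across a 4 week period". Section 6.1 has two weeks of checklists and then "At the end of four weeks all participants will be sent a second set of questionnaires via email to complete". Section 6.2 has a two-week period, a post-treatment battery and a one-month follow-up. Section 9.1 gives six weeks in total, yet says "This will include an initial questionnaire battery, four week manipulation assessment period, and the post-treatment" questionnaires and a one-month follow-up.

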18.0 Provisions to Monitor the Data to Ensure the Safety of Subjects*

NA

19.0 Provisions to Protect the Privacy Interests of Subjects

19.1 To facilitate privacy, participants will be informed that they can decline to answer any questions they do not wish to.

Participants will not have access to responses to any questionnaire from any other participants, nor will future participants have access to the current participant's responses.

19.2 Participants are explained the limits of confidentiality and are told they do not have to answer any questions they do not want to.

19.3 The aforementioned Key-file will contain identifying information (e.g., subject name, contact information) and study Identification Code numbers. This list will be kept separate from all other study data and will be password protected. Only study personnel will be given the password to this Key-file by the PI. All other data will contain Identification Code numbers only—no identifying information will be listed on any other data.

20.0 Compensation for Research-Related Injury

20.1 We do not anticipate any risk of research related injury to our participants.

20.2 NA

21.0 Economic Burden to Subjects

21.1 We do not anticipate that participation in our study will cause any economic burden to our participants.

22.0 Consent Process

22.1 The participant will be given the opportunity to read through the consent form and give signed informed consent if they agree to participate. No data will be collected before consent is obtained.

23.0 Process to Document Consent in Writing

23.1 We will follow "SOP: Written Documentation of Consent (HRP-091)."

24.0 Setting

24.1 Participation will involve completion of questionnaires and computer tasks on their personal computer.

25.0 Resources Available

25.1 Costs of research are estimated to be minimal and will be covered by funds from the [name] Lab.

- *The research group has had success in the past recruiting student populations for online and in person studies including intervention studies.*
- *The researchers will have access to the research group lab space located on the Florida State University Campus, which will provide the necessary staff, equipment, and materials.*
- *All research personnel will complete the required Human Subjects Training and will be asked to demonstrate competence with the procedures per the standards of the study prior to their involvement. They will receive supervision and training from the graduate student overseeing the project regarding the study protocol, procedures, and their duties. All study personnel will also be trained to deal with sensitive clinical issues and will be available during the assessment process should participants need assistance.*
